6.5.2. Analytical Methods

Plasma PK sample analyses will be performed using validated procedures and methods at AIT Bioscience.

6.6. Pharmacodynamic Assessments

6.6.1. MDS-UPDRS

See [Section 6.4.8](#).

6.6.2. Assessment of ON

Subjects will provide a self-assessment of their ON or OFF state, and Investigators will provide an assessment of the ON or OFF state of the subject, at the time points delineated in the Study Schedule in [Table 1](#).

7. STUDY SCHEDULE

7.1. Screening (Up to 21 Days Prior to Visit 3 Dosing) (Visit 1)

(Refer also to study synopsis and [Table 1](#))

Prior to enrolling in the study, and before performing any study-related procedures, potential subjects will attend the first of two Screening Visits, at which time they will be provided with full information concerning details of the study assessments and procedures. They will also be provided with the Subject Information Sheet and Informed Consent Form. Prior to being asked to sign the consent form, subjects will be given time to review study information and ask any questions.

After the consent form is signed, Screening assessments will be carried out as follows:

- Review of medications, medical history and inclusion/exclusion criteria.
- Administer MMSE (if required) to confirm eligibility
- Record of pre-treatment AEs.
- Measurement of height and weight.
- Recording demographic information.
- Complete physical examination (including nasal examination), including full MDS-UPDRS (see [Appendix 4](#)).
- 12-Lead ECG.
- Vital signs (blood pressure [supine and standing]; and heart rate, respiratory rate and oral temperature [supine only]).
- Clinical laboratory testing (non-fasting haematology, serum chemistry and urinalysis).
- Serum pregnancy test (WOCBP only).
- FSH (post-menopausal women only).

Due to variability in assessment length, assessments collected out of window, with the exception of PK samples and UPDRS, will not be considered deviations.

7.2. Admission to Clinic (Day prior to Visit 2 and Visit 3)

Depending on private arrangements, capability, and logistics, subjects may be domiciled in the study clinic from the evenings prior to Visit 2 and Visit 3. Subjects will receive a standard meal and snacks and be offered a light breakfast in the morning before dosing and thereafter may be offered a standard meal and/or snacks. Subjects will not complete any study procedures until the morning of both Visit 2 and Visit 3.

7.3. Evaluation of Dopamine Responsiveness (Screening [Visit 2])

Subjects considered eligible for study participation as per the outcome of Screening (Visit 1) are to return to the study clinic for Screening (Visit 2) on one day between Screening Visit 1 and Day 0 (Visit 3), i.e. within the maximum 21-day Screening window.

For this visit (Visit 2), the subject will suspend their usual anti PD medication from 22:00 pm the previous evening (including any DCIs). If not domiciled, they should arrive at the clinical research site in an OFF state, which will be confirmed and characterised by full MDS-UPDRS assessment. The subjects will then have a light breakfast 30 minutes before they take their usual L-dopa containing medication (including any rescue medication they would normally take for an OFF episode) and repeat the MDS-UPDRS Part III (motor examination) tests only at +15, +30, +45, +60, +90 and +120 minutes thereafter for Cohorts 1, 2 and 3, and +30, +60, +90 and +120 minutes for Cohort 4.

Subjects showing at least a 30% improvement in MDS-UPDRS Part III score during this visit will be deemed to be dopamine responsive, will be eligible to be randomized and will proceed to Visit 3/Day 0.

If the subject normally responds (subjective) to their dopaminergic medication but has an unexpectedly poor response (<30%) at Visit 2, which although unexpected could be explained (e.g. due to slow gastric emptying), then the dopamine responsiveness assessment may be repeated prior to Visit 3.

Data from screen failures at the Visit 2 (dopamine responsiveness visit) will be collected and reviewed but data from screen failures at Visit 1 will not be recorded in the eCRF. Reasons for screen failures will be collected in study Screening logs.

7.4. Dosing and Admission to Clinic (Day 0) (Visit 3)

7.4.1. Before Dosing

Subjects not domiciled in the study clinic on the evening of Day -1 will be transported to the study clinic as early as possible on the morning of Day 0.

All subjects, irrespective of date or time of arrival at the study clinic, will have their usual anti-PD medication (e.g. usual regular Madopar® dosing and any required anti-OFF treatment [e.g. Madopar rapid]) withheld from 22:00 on the evening before Day 0 until at least 120 minutes post-dosing with INP103 or placebo. Subjects determined as being in an ON state during the pre-dose assessments will not participate further in the study.

At visit 3, subjects will be offered, and encouraged to consume, a light breakfast, 30 minutes before dosing (and 15 minutes before pre-dose PK blood draw).

Pre-dose PK sample will be obtained once an IV cannula has been inserted, approximately 15 minutes prior to INP103 or placebo dosing. Prior to dosing, subjects will be sequentially assigned a randomization number. The subject identification number will remain the same throughout the study.

Subjects will be offered standard meal and/or snacks after dosing as appropriate.

All subjects in Cohorts 1, 2 and 3 will receive oral benserazide (25 mg) 60 ± 5 minutes before INP103 or placebo dosing.

Subjects in Cohort 4 will not receive oral benserazide but will be dosed with INP103 (with carbidopa) or placebo once OFF state confirmed and all other baseline assessments have been completed.

The following assessments will be carried out prior to dosing (in an order consistent with site's standard practice) on Day 0:

- Review to determine whether the subject continues to satisfy the study inclusion and exclusion criteria
- Vital signs (blood pressure [supine and standing]; and heart rate, respiratory rate and oral temperature [supine only])
- 12-Lead ECG
- Complete physical examination including nasal inspection
- Safety laboratory analysis sample collection (haematology, clinical chemistry and urinalysis)
- Urine pregnancy test (WOCBP only)
- Record of pre-treatment AEs (post randomization, pre-treatment emergent, including rating of dyskinesias)
- Review of the subject's concomitant medications, including non-prescription medications
- Investigator and subject self-evaluation of ON/OFF
- Full MDS-UPDRS assessment (I to IV)
- Administration of Benserazide (**60 ± 5 minutes before INP103 or placebo dosing – Cohorts 1, 2 and 3 only**)
- Blood sample collection for baseline PK readings (**within 15 minutes prior to dosing**) (see [Table 1](#)).

Due to variability in assessment length, assessments collected out of window, with the exception of PK samples and UPDRS, will not be considered deviations.

7.4.2. Dosing (Visit 3)

Subjects will be dosed by delegated clinic staff and according to the treatment arm to which they have been randomized. Additional details about the preparation and dosing of INP103 or placebo are provided in the Pharmacy Manual.

7.4.3. After Dosing

The subjects will remain in the study clinic post-dose through to the completion of all scheduled post-dose procedures 240 minutes after dosing.

The subject's usual rescue (anti-OFF [e.g. Madopar rapid]) medication will be permitted from 120 minutes post-dose (once all 120 minute assessments have been completed, but can precede ECG, physical examination and subject questionnaire) – if they are still OFF. In addition, subjects should take their regular anti PD medication (e.g. their regular morning Madopar dose) at 120 minutes post dosing whether or not they have returned to ON.

The following in-patient assessments will be performed after dosing:

1. Adverse Events (including overall dyskinesia rating) and concomitant medications will be continually monitored post-dose.
2. Vital signs will be measured at 30, 60 and 120 minutes post-dose. Blood pressure (supine and standing) and heart rate, respiratory rate and oral temperature (supine only) will be measured at all time points. Vital signs will be collected after MDS-UPDRS assessment (where both procedures are scheduled at the same time point) and will not be deemed protocol deviations if they occur outside the time window at each timepoint.
3. PK blood samples will be collected at 4, 9, 14, 29, (all + 1 minute) 44, 59, 89 and 119 (all \pm 2 minutes at each timepoint) minutes post-dose and will precede UPDRS assessments.
4. MDS-UPDRS III only at 15, 30, 45, 60, 90 and 120 minutes post-dose for Cohorts 1, 2 and 3) and 30, 60, 90, 120 minutes for Cohort 4 (\pm 2 minutes at each timepoint)
5. Investigator and subject self-assessment of ON/OFF at 30, 45, 60, 90, 120 and 240 minutes post-dose (\pm 10 minutes at each timepoint)
6. At 120 minutes, the subject's usual morning dose of all Parkinson's medications should be given following completion of assessments 1-5, regardless of ON/OFF state. In addition, if subject is still OFF, their usual OFF medication may be given (prior to completing assessments 7, 8 and 9).
7. Directed physical examination (including nasal inspection) will be performed at 120-180 minutes post-dose

8. 12-Lead ECG will be performed at 120-180 minutes post dose. In cases where vital signs are scheduled at the same time point, ECG will be completed in sequence with vital signs per the usual practice of the study sites.
9. Subject questionnaire will be completed as the last assessment from 120-180 minutes post-dose

Due to variability in assessment length, assessments collected out of window, with the exception of PK samples and UPDRS, will not be considered deviations.

Subjects will be discharged from the study site following satisfactory completion of assessments.

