Evaluation of ON/OFF (Investigator and self-assessment)		X		X					X	X	X	X	X	X				
Rescue OFF Tx allowed													X					
Usual morning anti-PD medication													X					
MDS-UPDRS Full ^h	X	X ^h		X											X			
MDS-UPDRS (III) motor (Cohorts 1 through 3)		X ⁱ						X ^j	X ^j	X ^j	X ^j	X ^j	X ^j					
MDS-UPDRS (III) motor (Cohort 4)		X ⁱ						X ^j		X ^j	X ^j	X ^j						
Prior and Concomitant Medications	X			X		CONTINUOUS												
Subject Questionnaire ^k													X					
Light Breakfast Offered		X		X														

Visit	1	2	3											4	
Day	Up to -21	Up to -20 to -1	-1	0											7
Window	N/A	N/A	N/A				See Footnotes (and Section 7.4.3)							± 10 mins	± 2 days ^a
Time (min)				Pre-dose	0	5	10	15	30	45	60	90	120	240	
Visit	Screening	Dopamine response	Treatment											Follow-up	
PK Blood Collection ¹ (Cohorts 1 through 3)				X					X		X	X	X		
PK Blood Collection ¹ (Cohort 4) Collected 1 minute prior to timepoint				X		X	X	X	X	X	X	X	X		

^a A +4 day window may be permitted in exceptional circumstances.

^b Prior to V2 and/or V3, subjects may attend the unit the previous evening and be domiciled overnight to allow early morning confirmation of their OFF state and facilitate scheduling of pre and post dosing procedures. Subjects not attending the unit the previous evening will arrive on Day 0.

^c Randomization may be performed on the day of dosing (Day 0) or the evening before (Day -1) for subjects being housed overnight prior to dosing.

^d Subjects should be rested in a recumbent position for ≥ 3 minutes prior to recording of ECGs. Subjects should be supine for at least 3 minutes prior to determination of supine vital signs (including blood pressure), after which they should stand and have only standing blood pressure measured immediately. Staff should be on hand to support subjects if required. ECGs and vital signs should be assessed after UPDRS assessment and PK blood draws. Sites may follow their usual sequence of procedures for recording vital signs and ECG where they occur together. The window allotted for vital signs will be +15 minutes at the 30 and 60 minute post-dose timepoints. The vital signs and ECG collection at 120 minutes may occur up to 180 minutes. Due to variability in assessment length, assessments collected out of window, with the exception of PK samples and UPDRS, will not be considered deviations.

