11.6. ECG Evaluations

All individual ECG parameter values (Heart Rate [bpm], QT interval [msecs], PR interval [msecs], QRS interval [msec], RR interval [msecs], QTcF [msecs], and QTcB [msecs]) and overall ECG clinical interpretation will be presented in data listing. Observed ECG parameter values and changes from baseline (prior to the first study drug administration [benserazide or INP103/placebo]) will be summarized by treatment and protocol specified collection time point.

In addition, clinical assessment of the ECG (Normal, Abnormal NCS, and Abnormal CS) will be summarized by cohort and treatment group and protocol specified collection time point, using frequency tabulations.

Furthermore, the proportion of subjects meeting the following criteria based on QTc values (defined both using the correction by Bazett and by Fridericia) will be summarized by treatment group, using frequency tabulations:

- QTc value >500 msec
- QTc value increasing >15% from baseline if baseline value is ≥ 440 msec
- QTc value increasing >30% from baseline if baseline value is <440 msec
- QTc value increasing >30% from baseline
- QTc value increasing >60% from baseline

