11.7.3. Orthostatic hypotension

The proportion of subjects experiencing orthostatic hypotension will be summarized by cohort and treatment group and protocol specified collection time point, using frequency tabulations, if applicable.

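### The directed exam and the only Visit 3 post-dose ECG may follow usual PD medication and rescue, yet the SAP tabulates them by treatment without regard to that medication

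*Protocol*

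**What the plan says.** **Protocol 7.4.3** numbers the post-dose procedures. Vital signs are item 2 and the ON/OFF assessments item 5. Item 6 is medication: the usual morning Parkinson's drugs "should be given following completion of assessments 1-5, regardless of ON/OFF state". Subjects still OFF may add their usual rescue, and the same section allows this "once all 120 minute assessments have been completed, but can precede ECG, physical examination and subject questionnaire". Items 7 and 8 come next: "Directed physical examination (including nasal inspection) will be performed at 120-180 minutes post-dose", and "12-Lead ECG will be performed at 120-180 minutes post dose".

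**Protocol Table 1, footnote d** adds: "The vital signs and ECG collection at 120 minutes may occur up to 180 minutes". Protocol section 6 says that late assessments other than PK samples and UPDRS do not count as deviations.

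**SAP 11.6** covers "Observed ECG parameter values and changes from baseline", summarised by treatment at each scheduled time point, and gives QTc outlier proportions by treatment group. SAP 11.7.4 does the same for new abnormal examination findings, by cohort, treatment group and time point. SAP 11.7.3 states: "The proportion of subjects experiencing orthostatic hypotension will be summarized by cohort and treatment group", again by time point. SAP 8.5.4 applies no visit windows. SAP 9.5 lists rescue and usual morning medication and tabulates each as yes or no; neither is linked to a safety measurement.

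**The concern.** ECG, physical examination and vital signs are primary endpoints (Protocol 3.1, SAP 3.2.1), and the primary objective is a comparison with placebo (SAP 3.1.1). The comparison is cleanest while placebo subjects have had no L-dopa that day. Once the 120-minute medication has been taken, that no longer holds. Protocol section 3 puts the usual morning L-dopa dose at 50-250 mg, against study doses of 35-140 mg, so a placebo subject's ECG may follow more L-dopa than some active subjects received as study drug.

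There are two effects. The usual dose goes to everyone. It adds variation and can dilute a difference, for example where a threshold criterion is then met in both arms. Rescue is given only to subjects still OFF, which is an outcome after randomisation. If its use differs by arm, the comparison can also be biased.

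**Working it through.** The plan states no figure on this point. The check is of procedure order against analysis rules.

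**1. Longest gap.** The medication is due at 120 minutes and the windows close at 180 minutes: 180 - 120 = 60 minutes.

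**2. Visit 3 post-dose measurements certain to precede the medication**

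| Measurement | Planned times (min) | Certain to precede |
|---|---|---|
| 12-lead ECG | one, at 120-180 | 0 of 1 |
| Directed exam | one, at 120-180 | 0 of 1 |
| Vital signs, 7.4.3 order | 30, 60, 120 | 3 of 3 |
| Vital signs, footnote d | 30, 60, 120 (to 180) | 2 of 3 |

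Table 1 shows no other post-dose ECG until the Day 7 visit.

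**3. Vital signs.** Item 2 comes before item 6, and 7.4.3 does not name vital signs among the procedures that rescue may precede. Footnote d nevertheless lets the 120-minute set run to 180 minutes. Item 8 also lets sites sequence ECG and vital signs by their own practice when the two coincide. A site following footnote d could therefore measure standing blood pressure after the medication without a recorded deviation. The passages do not agree.

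**4. Analysis.** With no windows, a result obtained at 180 minutes stays under the 120-minute label. Nothing in SAP 11.5-11.7 conditions on the medication recorded under SAP 9.5.

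**5. What a bias calculation would need.** Let r_A and r_P be the proportions taking rescue on active and placebo, f the fraction of measurements made after rescue among those who take it (taken as equal in both arms), and d the change in event probability due to rescue. The distortion of the active-minus-placebo difference is then f x (r_A - r_P) x d. The documents give none of these four quantities. For 120-minute orthostatic hypotension, f = 0 if the 7.4.3 order is followed.

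**6. Scale of the tables.** One subject is 1/6 = 16.7 points in an active group of 6, or 1/9 = 11.1 points in Cohort 4 at its maximum. Pooled placebo has 4 x 2 = 8 subjects, or 9 if Cohort 4 is over-enrolled: 1/8 = 12.5 or 1/9 = 11.1 points.

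**The case against.** The strongest reply is that little is hidden. The SAP makes no causal claim: it has no formal hypotheses (3.3) and does no inferential safety testing (11). Vital signs and orthostatic hypotension are shown by time point, so the 30- and 60-minute values already stand apart from any later medication. Rescue, morning medication, ECG, examination and vital signs are all listed by subject, and with 32 to 36 subjects a reader could match the listings by hand. The protocol also permits rather than requires medication first; an ECG at 120 minutes before it is equally allowed. Splitting groups of 6 gives very small cells that are no longer randomised comparisons.

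Most of this stands, and it limits the point. It does not remove it. Descriptive tables are all that the primary safety comparison will have, and the planned ECG and exam tables mix results from before and after L-dopa without saying so. Matching by hand is possible but not planned.

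A reader might go further and infer that the orthostatic hypotension comparison is biased toward no harm by a calculable amount. The documents do not support that: 7.4.3 places those measurements before medication, and any figure would need invented rescue rates and effects. Nor is this the only post-dose ECG on site, since subjects return to the institution for another on Day 7. It is the only one at Visit 3.

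**Conclusion.** The point holds for the ECG and the directed examination. Followed as written, the plan allows both to come after usual medication in all subjects, and after rescue in some, and the SAP reports them by treatment without distinction. Dilution of the placebo comparison is possible. Bias is possible if rescue differs by arm, which is plausible if INP103 works, but its size and direction cannot be computed from the documents. For 120-minute vital signs and orthostatic hypotension, the finding is an unresolved conflict between 7.4.3 and footnote d, not demonstrated confounding. The 30- and 60-minute values are sound. This is a low-cost improvement to the SAP. The conclusion rests on the order of procedures in the text; the documents do not show how often sites would medicate first.

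**What to change.** Leave the schedule and clinical management as they are.

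- In SAP 11.5-11.7, use recorded times to classify each Visit 3 ECG, examination, vital-sign and orthostatic result from the 120-180 minute period as before any PD medication, after usual medication only, or after usual medication plus rescue. A two-way before/after split would leave the rescue imbalance inside the after group.
- Show this status in the listings, and present the ECG, QTc and examination summaries by status beside the planned tables.
- Base the orthostatic comparison on the 30-minute, 60-minute and pre-medication 120-minute values.
- Reconcile footnote d with 7.4.3 on the 120-minute vital signs.

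The cost is one derived variable and a few extra tables. Cells will be small, pre-medication ECGs may be few, and the subsets are descriptive, so the split shows the problem but does not remove it. SAP 9.5 refers to medication dates or times, but the CRF is not among the documents. Confirm before the SAP is amended that it captures clock times for the medication and for each assessment.

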7.5. Follow-Up/End of Study (Day 7 + 2 days)

The subjects will return to the institution on Day 7 (+2 days). In exceptional circumstances, if a subject is unable to attend the end of study visit on Day 7 (+ 2 days, as indicated), the Investigator (or qualified designee) should discuss appropriate re-scheduling to a maximum of +4 days with the Sponsor's Medical Monitor (or appropriate designee). The following assessments will again be carried out:

- Adverse Events (including overall dyskinesia rating) and concomitant medications
- 12-Lead ECG
- Vital signs (blood pressure [supine and standing]; and heart rate, respiratory rate and oral temperature [supine only])
- Complete physical examination
- Clinical laboratory testing (haematology, serum chemistry and urinalysis)
- Full MDS-UPDRS

Due to variability in assessment length, assessments collected out of window, with the exception of PK samples and UPDRS, will not be considered deviations

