Subjects may be domiciled at the clinic overnight to enable scheduled assessments on the morning of, and prior to, Visit 2 (standard medications) and Visit 3 (test article) dosing, or will have transport provided to ensure they arrive at the clinical research unit on the morning of Visit 2 and Visit 3. Regardless of time of arrival at the study site, all subjects will be required to suspend dosing of usual PD medication (e.g. regular Madopar® or Sinemet® doses, DAs and/or COMT inhibitors doses and any required anti-OFF medication [e.g. Madopar rapid]) from 22:00 pm on Day -1, the day prior to study dosing. Suspension of usual PD medication will include on the morning of Day 0.

On Day 0, upon arrival at the research site (or upon waking if the subject was domiciled overnight at the research unit), and at 60 ± 5 minutes before dosing with INP103 or placebo, all subjects in **Cohorts 1, 2, and 3** will take oral benserazide hydrochloride (benserazide) 25 mg (provided by the Sponsor). Subjects in **Cohort 4** will NOT receive oral benserazide. Subjects who arrive at the study site on Day 0 (or who were domiciled overnight) and are determined by the Investigator to be in an ON state up to the scheduled time of dosing will not be dosed and will be excluded from further study participation but may be replaced at Sponsor's discretion.

On their scheduled day of dosing (Day 0; or on arrival at the unit on Day -1), eight subjects in each of three dose cohorts (35, 70 or 140 mg of INP103 L-dopa) and at least eight (8) (maximum 12) subjects in Cohort 4 (70/7.0 mg of INP103 L-dopa:carbidopa) will be randomized in a 3:1 fashion to one of two treatment arms. All subjects in Cohorts 1, 2 and 3 will receive oral benserazide 25 mg 60 ± 5 minutes before dosing with the study drug. Subjects in Cohort 4 will not receive oral benserazide before dosing with the study drug:

- INP103 (n=6 or maximum 9 in Cohort 4)
- Placebo (n=2 or maximum 3 in Cohort 4)

[figure not shown]
Use of usual anti-PD medication (usual regular dosing [e.g. regular Madopar or Sinemet] and use of anti-OFF treatment, if required) may resume at 120 minutes after use of INP103 or placebo.

Subjects will be monitored for 7 days after the final administration of INP103 or placebo. All subjects will be observed as in-patients for at least 240 minutes post-dosing at visit 3. Follow-up evaluations will occur 7 days after dosing.

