3.1. Primary Endpoints

Safety and tolerability, including the assessment of physical examinations (including nasal inspection), electrocardiograms (ECGs), vital signs (including supine and standing blood pressure, all other vital signs supine only), clinical laboratory results, and AEs (specifically, levodopa induced dyskinesia assessment, see [Section 6.4.2](#)) over the immediate 240 minutes following dosing and over 7 days of follow-up.

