8. ADVERSE EVENTS

In this study, AEs will be reported for all subjects from signing of consent until the completion of the end of study Day 7 follow-up visit. SAEs will be reported in all subjects (enrolled and not enrolled) from the time of consent. Treatment-emergent AEs (TEAEs) will be reported from dosing on Day 0. Study procedure-related AEs will be evaluated specifically from the time of consent until INP103 or placebo administration. Treatment-emergent AEs will be evaluated from INP103 or placebo dosing until the end of study visit. AEs that are ongoing at the end of study visit will be marked as ongoing on the AE eCRF page.

All AEs resulting from spontaneous subject self-reporting, direct enquiry or observation by study staff, will be recorded in the subject's medical records and the eCRF.

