11. Laboratory test abnormalities at Screening (Visit 1) deemed clinically significant by the Investigator.
12. History or presence of alcoholism or drug abuse within the 2 years prior to INP103 or placebo dosing
13. Administration of an investigational product in another trial within 30 days or 5 half-lives (whichever is longer) prior to INP103 or placebo dosing
14. Significant nasal congestion, physical blockage in either nostril, or significantly deviated nasal septum as evaluated by the PI or other suitably trained healthcare professional.
15. Subjects who have previously shown hypersensitivity to L-dopa or benserazide (for Cohorts 1, 2, and 3), or L-dopa or carbidopa (for Cohort 4) or any of their excipients

Investigational product, dosage and mode of administration:

INP103 is a drug-device combination product containing a drug component, L-dopa, and device component, the I231 Precision Olfactory Delivery (POD) device. In Cohorts 1, 2, and 3, L-dopa will be administered intranasally in single doses of one (35 mg), two (70 mg) or four (140 mg) puffs of INP103, 60 minutes after oral benserazide hydrochloride 25 mg.

In Cohort 4 the INP103 formulation will contain L-dopa:carbidopa in a 10:1 ratio (70 mg L-dopa and 7.0 mg carbidopa (2 capsules)). Dosing will take place once OFF episode is confirmed and will not include pre-dosing with oral benserazide.

Duration of treatment:

This is a single dose study. The total duration per subject from Screening (Visit 1) to follow-up (Visit 4) is up to 30 days.

Reference therapy, dose and mode of administration, batch number:

Placebo is an inert, visually similar product without L-dopa or carbidopa (microcrystalline cellulose).

Criteria for evaluation:

Once dosing has been completed (for all 8 subjects) in a cohort (Cohorts 1, and 2), data will be collected through to 7 (\pm 2) days post dosing (Visit 4, follow-up). This data will then be reviewed by a Safety Monitoring Committee (SMC) and if no INP103 or placebo-related serious adverse events (SAEs) or severe AEs have been reported, dosing may commence in the next cohort. The SMC will have 7-14 days between dosing of cohorts to review safety data compiled by the site and the biostatistics analysis provider.

Statistical methods:

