Once dosing has been completed (for all subjects) in a cohort, data will be collected through to 7 days post dosing (Visit 4, follow-up). This data will then be reviewed by a Safety Monitoring Committee (SMC) for cohorts 1 and 2 only, and if no INP103 or placebo-related serious adverse events (SAEs) or severe AEs have been reported, dosing may commence in the next cohort. The SMC will have 7-14 days between dosing of cohorts to review safety (and available PK data) compiled by the site and the biostatistics analysis provider.

Interim analysis of data will be conducted upon completion of Cohort 1 and 2 study procedures, at the discretion of the Sponsor, depending on rate of recruitment. In this scenario, Cohort 1 and 2 data will be soft-locked, patients may be unblinded and tables, listings, and figures of collected data will be produced. Unblinding of Cohort 1 and 2 data will not jeopardize blinding of any enrolled Cohort 3 or 4 subjects at the time of the interim analysis.

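### Visit 4 has conflicting windows (Day 7 +2 in section 7.5, Day 7 ±2 in Table 1 and the SAP synopsis), so a visit that complies with the schedule can end routine AE collection before the 7 days in the primary endpoint

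*Protocol*

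**What the plan says.** Protocol section 7.5 states the Visit 4 window in its heading and twice in its text, each time on the late side only: "The subjects will return to the institution on Day 7 (+2 days". It adds an exceptional extension to +4 days. The table of contents entry for 7.5 agrees.

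Protocol Table 1 gives the Day 7 column a window of ±2 days, repeated on successive pages of the table. Its footnote a extends only the late side: "A +4 day window may be permitted in exceptional circumstances". Protocol section 6 directs sites to complete visits according to Table 1.

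The SAP differs within itself. The synopsis, describing the data that go to the Safety Monitoring Committee (SMC) for Cohorts 1 and 2, says "data will be collected through to 7 (\pm 2) days post dosing". SAP section 4 gives the same step with no window: "data will be collected through to 7 days post dosing (Visit 4, follow-up". SAP 4.3 refers clinical assessments to protocol section 7, which contains the +2 rule.

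Two further statements fix what the visit has to deliver. The primary endpoint is safety "over the immediate 240 minutes following dosing and over 7 days of follow-up" (protocol 3.1), and section 3 says "Subjects will be monitored for 7 days after the final administration of INP103 or placebo". Collection, however, is tied to the visit and not to a day: "AEs will be reported for all subjects from signing of consent until the completion of the end of study Day 7 follow-up visit" (protocol section 8). The same section evaluates TEAEs up to the end of study visit, and SAP 11.1 counts them to the end of the study.

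**The concern.** The two protocol windows agree on the late side and conflict only on the early side. The early side decides whether a subject is observed for the full endpoint period. A site working from Table 1 can see a subject on Day 5, be within window, and finish routine AE reporting then. No later contact is scheduled.

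The analysis would not reveal this. SAP 8.5.4 applies no visit windows, so a Day 5 visit is summarised as the follow-up visit. That is an ordinary convention, but it means the tables will not separate early visits from visits on Day 7. The deviation rule does not settle the matter either. Section 7.5 exempts out-of-window assessments other than PK and UPDRS. A full MDS-UPDRS on Day 5 would therefore be a deviation under section 7.5 and compliant under Table 1.

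Visit 4 is also the only scheduled post-discharge ECG, vital signs, laboratory and nasal examination, and its data go to the SMC before Cohorts 2 and 3.

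**Working it through.** **Inputs** (dosing = Day 0, as in the protocol)

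- Section 7.5: nominal Day 7, early allowance 0, late allowance 2, exceptional late allowance 4.
- Table 1: nominal Day 7, early allowance 2, late allowance 2, exceptional late allowance 4 (footnote a).
- Primary endpoint and planned monitoring: 7 days.
- End of AE and TEAE collection: Visit 4.

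**The plan's own figure.** The only stated number that depends on the visit's timing is the maximum time per subject from screening to Visit 4.

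- Protocol synopsis, 28 days: 21 + 7 = 28, which allows no late window.
- SAP synopsis, 30 days: 21 + 7 + 2 = 30.
- With the exceptional extension: 21 + 7 + 4 = 32.

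Both stated figures are reproduced. Neither helps choose between the windows, because the late allowance is +2 in both.

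**Permitted AE follow-up**

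| | Section 7.5 | Table 1 |
|---|---|---|
| Earliest visit | 7 − 0 = Day 7 | 7 − 2 = Day 5 |
| Latest visit | 7 + 2 = Day 9 | 7 + 2 = Day 9 |
| Spread; ratio | 9 − 7 = 2 days; 9/7 = 1.29 | 9 − 5 = 4 days; 9/5 = 1.8 |
| Latest with exception | 7 + 4 = Day 11 | 7 + 4 = Day 11 |
| Spread; ratio with exception | 11 − 7 = 4 days; 11/7 = 1.57 | 11 − 5 = 6 days; 11/5 = 2.2 |

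**Shortfall against the endpoint.** At the earliest Table 1 visit it is 7 − 5 = 2 days, and 2/7 = 28.6% of the stated period. Under section 7.5 it is zero.

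**From time to events (illustration only).** The documents give no AE rate. Assume a constant hazard and every subject seen on Day 5. Incidence observed by Day 5 is then p5 = 1 − (1 − p7)^(5/7):

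- p7 = 10%: p5 = 7.2%
- p7 = 20%: p5 = 14.7%
- p7 = 30%: p5 = 22.5%

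If events cluster soon after the single dose, the loss is smaller than this.

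**The case against.** The strongest case on the other side is that this is a clerical mismatch with little effect on the results. Most of its parts stand as limits on the size of the problem.

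- *A reader might infer that all AE collection can stop on Day 5.* The documents do not support that. Section 8 gives SAE reporting a start at consent and no stated end. Section 8.7 follows AEs judged related to resolution or stabilisation. The design sections separately call for 7 days of monitoring. The gap is limited to new non-serious AEs that start between an early visit and Day 7.
- *A reader might infer that 29% of the safety information is lost.* That figure is calendar time. This is a single-dose study with at least 240 minutes of in-patient observation, and section 1.4 expects any irritancy to be transient.
- *A reader might infer that dose escalation is compromised.* The criterion in protocol section 3 is related SAEs or severe AEs. Only a non-serious severe AE first appearing after an early visit and by Day 7 could be missed, and nothing in the documents suggests such events are expected.
- *A reader might infer that the treatment comparison is biased.* Randomisation and blinding give no reason for early visits to differ by arm, and SAP section 11 plans no inferential safety testing.
- *A reader might infer that the SAP as a whole adopts ±2.* It does so in one synopsis sentence. SAP section 4 does not repeat it, and SAP 4.3 refers to protocol section 7.

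The objection does not remove the contradiction. Calling the visit the Day 7 follow-up shows the intent but sets no earliest date, and section 6 makes Table 1 the operative schedule. The monitoring statement supplies no contact at which a new event after an early visit would be collected. A reading error in the PDF is unlikely, since each form of the window recurs in its own place.

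**Conclusion.** The inconsistency is real and sites can act on it. Under Table 1 the minimum follow-up is 5 days, 2 days short of the primary endpoint. Under section 7.5 it is 7 days. Like for like, the ranges are 5 to 9 against 7 to 9 days, or 5 to 11 against 7 to 11 with the exception. Correcting the early side guarantees the stated 7 days. It does not make follow-up equal, since subjects could still differ by up to 4 days with the exception.

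The conclusion rests on two readings: that sites follow Table 1 as section 6 directs, and that AE collection closes at Visit 4 as section 8 says. How many visits would fall early, and how many events would be missed, cannot be determined from the documents. The number may be small. The point warrants a correction because the affected endpoint is the primary one and the change is minor. It does not call the safety conclusions into question.

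**What to change.** Change the Visit 4 window in Table 1 from ±2 to +2 days on every page where it appears, keeping footnote a. Make the same change in the SAP synopsis sentence on SMC data under the criteria for evaluation. Both then match section 7.5 and the 7-day endpoint. State the window in days after dosing, because the protocol calls dosing Day 0 and SAP 6.7.2 calls it Study Day 1.

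Keep the rule that TEAEs run to the end of study visit. A fixed count from Day 0 to Day 7 would drop later events that the plan deliberately includes. With a +2 window every in-window subject has at least 7 days, so an added telephone contact is not needed.

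As a minor separate correction, the protocol's maximum of 28 days per subject omits the +2 window. It should read 30, as in the SAP, or 32 if the exceptional +4 is to be covered, in which case the SAP's figure changes too.

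The cost is one table entry, one SAP phrase and the duration statement. The downside is slightly less flexibility in scheduling Visit 4.
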